## 5.6. Unscheduled Visits

Unscheduled visits may be performed at any time and for any reason, including those not specifically mentioned in this section, as deemed necessary by the Investigator.

Unscheduled visits conducted for the following reasons should include collection of AEs, clinical chemistry, hematology, concomitant medication collection, and vital signs:

- Management of an AE or SAE;
- Performance of additional laboratory tests for clinically abnormal laboratory test values or to confirm a possible pregnancy;
- Subject safety evaluation.

Unscheduled visits conducted for the following reasons do not require additional assessments unless deemed necessary by the Investigator:

- Study drug dispensation;
- Any operational need that would require the subject to return to the site between scheduled visits.

# 6. SAFETY REPORTING, MEDICAL MANAGEMENT, AND OVERSIGHT

To avoid inter-observer variability, every effort should be made to ensure that the same individual who made the initial baseline determinations completes all safety assessments. Safety parameters include vital sign measurements, ECG results, AEs, SAEs, weight, and laboratory test results.

## 6.1. Definition of Adverse Event

An AE is defined as any untoward medical occurrence in a subject regardless of its causal relationship to study drug. An AE can be any unfavorable and unintended sign (including any CS abnormal laboratory test result), symptom, or disease temporally associated with the use of the study drug, whether or not it is considered to be study drug related. Included in this definition is any newly occurring event or previous condition that has increased in severity or frequency since the administration of study drug.

The definition above, provided for in the good clinical practice (GCP) International Council for Harmonisation of Technical Requirements for Pharmaceuticals for Human Use (ICH) Guideline E6, is being extended for the purpose of Reata studies to include any events, intercurrent diseases and accidents observed while the subject is on study, ie, during the actual Treatment Period, as well as during drug-free, pre- and post-Treatment Periods.

All AEs observed or reported by the subject during the study (from the time of consent until the final visit or 30 days following final study dose for subjects who terminate early) must be reported, regardless of their relationship to study drug or their clinical significance. All conditions present prior to time of consent should be documented as medical history.

## 6.1.1. Definition of Non-treatment-emergent Adverse Event

Adverse events that present after signing of the ICF and prior to the initiation of study drug will be categorized as non-TEAEs and considered "not applicable" for the causality assessment with study drug.

## **6.1.2.** Definition of Treatment-emergent Adverse Event

Adverse events that present, or worsen in intensity or frequency, following the initiation of study treatment will be categorized as TEAEs.

## 6.2. Definitions of Serious Adverse Event

An SAE is any AE occurring at any dose and regardless of causality that:

- Results in death
- Is life-threatening
- Requires inpatient hospitalization or prolongation of existing hospitalization
- Results in persistent or significant incapacity or substantial disruption of the ability to conduct normal life functions

- Is a congenital anomaly or birth defect in an offspring of a subject taking study drug
- Is an important medical event

The term "life-threatening" refers to an event in which the subject was at immediate risk of death at the time of the event. It does not refer to an event that hypothetically might have caused death if it were more severe.

Important medical events are those that may not meet any of the criteria defined above; however, they may be considered serious when, based upon appropriate medical judgment, they may jeopardize the subject and may require medical or surgical intervention to prevent one of the other outcomes listed in the SAE definition.

Pregnancy is not considered an AE; however, information will be collected for any pregnancies that occur during the study (from the time of consent until the final visit). Certain pregnancy outcomes will require submission as an SAE (Section 6.6).

## **6.3.** Recording of Adverse Events

At every study visit, subjects must be asked a standard, non-directed question, such as, "How do you feel?" or "How have you been feeling since your last visit?" to elicit any medically related changes in their well-being. They will also be asked if they have been hospitalized, had any accidents, used any new medications, or changed concomitant medication regimens (including prescription drugs, over-the-counter medications, vitamins, herbal products, and minerals). Responses should be recorded in the source documents.

In addition to subject observations, AEs must be documented for any clinically significant diagnosis resulting from abnormal laboratory test values, physical examination findings, ECG abnormalities, or other documents that are relevant to subject safety.

Adverse events resulting from concurrent illnesses, reactions to concurrent illnesses, reactions to concurrent medications, or progression of disease states must also be reported. Pre-existing conditions (present before the start of the AE collection period, prior to signed consent) are considered concurrent medical conditions and should NOT be recorded as AEs. However, if the subject experiences a worsening or complication of such a concurrent condition, the worsening or complication (except disease progression) should be recorded as an AE. Investigators should ensure that the AE term recorded captures the change in the condition (eg, "worsening of...").

Elective procedures (surgeries or therapies) scheduled prior to the start of AE collection should not be recorded as AEs but rather documented in the subject's source documents as elective (eg, elective periodontal surgery). However, if a preplanned procedure is performed early (eg, as an emergency) because of a worsening of the pre-existing condition, the worsening of the condition should be captured as an AE.

While an AE is ongoing, changes in the severity (eg, worsening or improving) should be noted in the source documents but when documenting the AE, only the total duration and greatest severity should be recorded in the eCRF. Adverse events characterized as intermittent require documentation of onset and duration.

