## 6.3.4. Assessment of Causality

The relationship of an AE to the administration of the study drug is to be assessed according to the following definitions:

Unrelated: This relationship suggests that there is no association between the study drug and the reported event.

Unlikely: This relationship suggests that the temporal sequence of the event with study drug administration makes a causal relationship improbable and/or other factors also provide plausible explanations.

Possible: This relationship suggests that treatment with the study drug caused or contributed to the AE. That is, the event follows a reasonable temporal sequence from the time of study drug administration and/or follows a known response pattern to the study drug but could have been produced by other factors.

Probable: This relationship suggests that a reasonable temporal sequence of the event with study drug administration exists and based upon the known pharmacological action of the drug, known or previously reported adverse reactions to the drug or class of drugs, or judgment based on the Investigator's clinical experience, the association of the event with study drug administration seems likely.

Definitely: This relationship suggests that a definite causal relationship exists between the study drug administration and the AE, and other conditions (eg, concurrent illness, progression/expression of disease state, or concurrent medication reaction) do not appear to explain the event.

Not Applicable: AE occurred prior to administration of first dose of study drug.

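### Protocol 6.3 requires adverse events from disease progression to be reported, then excepts undefined disease progression from recording, so sites may record the same clinical worsening differently

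*Protocol*

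**What the plan says.** One paragraph of Protocol 6.3 gives three instructions in sequence:

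1. "Adverse events resulting from concurrent illnesses, reactions to concurrent illnesses, reactions to concurrent medications, or progression of disease states must also be reported".
2. Conditions present before consent "are considered concurrent medical conditions and should NOT be recorded as AEs".
3. If such a condition worsens or leads to a complication, "the worsening or complication (except disease progression) should be recorded as an AE".

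The available protocol text does not define disease progression, say whether it means the neuropathy, the diabetes or any condition, or explain how to tell it from a worsening that must be recorded.

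The neighbouring rules carry no such exception:

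- Protocol 6.1 counts "any newly occurring event or previous condition that has increased in severity or frequency since the administration of study drug" and requires every AE to be reported, whatever its cause or clinical importance.
- Protocol 6.1.2 treats an event that worsens after treatment starts as treatment-emergent. SAP 7.1 does the same for events already present before the first randomized dose.
- Protocol 5.1.4 sends relevant changes after Screening to the eCRF as AEs. Protocol 4.6.1 does so for new clinically relevant findings.
- The next paragraph of 6.3 deals with a planned procedure brought forward "because of a worsening of the pre-existing condition, the worsening of the condition should be captured as an AE".
- Protocol 6.3.4 names "progression/expression of disease state" among the alternative explanations weighed when causality is assessed.

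**The concern.** Under the inclusion criteria every subject has diabetes and DPNP, so the exception can be invoked for anyone in the trial: about 192 subjects in Part 1 and 384 over both parts. A clinical worsening of the neuropathy or of another diabetic complication is a worsening of a pre-existing condition, and an investigator may also reasonably call it progression. A site guided by the first sentence, or by 6.1, records it. A site guided by the exception does not.

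The frequency of AEs and SAEs is part of the primary safety endpoint (Protocol 2.2.1.2). Whether a worsening is due to the disease or to the drug is a question for the randomized comparison with placebo. The exception lets that judgement be made by the investigator before anything is recorded, and the SAP can analyse only what is recorded.

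**Working it through.** The plan states no figure on this point, so the check is a comparison of the rules, followed by a note on scale.

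**Step 1. Apply each rule to one case.** A subject with DPNP is found to have new sensory loss at a treatment-period examination, and the investigator thinks it is the disease advancing.

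| Rule | Recorded as an AE? |
|---|---|
| Protocol 6.3, sentence on progression of disease states | Yes |
| Protocol 6.3, sentence on worsening or complication | No, if called disease progression |
| Protocol 6.1 | Yes, an increase in severity of a previous condition |
| Protocol 5.1.4 and 4.6.1 | Yes, if a relevant change or new clinically relevant finding |
| Protocol 5.2.3 | Yes, if it meets the AE definition |
| SAP 7.5 | Yes, if clinically significant |
| Protocol 6.3.4 | Presumes a record: progression is weighed when the AE is attributed |

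Only one rule gives No, and it stands in the same paragraph as a rule that gives Yes.

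**Step 2. Would the event reach the analysis another way?** In the visible Schedule of Assessments the MNSI is done only at Screening, so it cannot show change on study. A diabetic eye examination appears only as a randomization criterion (Protocol 4.2.1). Protocol 8.4.8 plans summaries of change in physical examinations, but SAP 7.5 brings examination findings into the Part 1 analysis through AEs. New sensory loss and worsening retinopathy therefore depend mainly on the AE record. Parts of the schedule and of the endpoint lists are blacked out, so this step rests on the visible text.

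**Step 3. Follow it to SAEs.** Protocol 6.2 defines an SAE as an AE that meets a seriousness criterion. If a hospitalised diabetic complication is held not to be an AE, then on that reading it is not an SAE, and the 24-hour report in 6.4 is not triggered. Section 6.2 has no safeguard for excluded progression.

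**Step 4. Scale.** With 64 subjects per arm, one subject is 1/64 = 1.6% and two are 2/64 = 3.1%. SAP 7.1 tabulates preferred terms with incidence of at least 2%, which is 0.02 × 64 = 1.28 subjects if applied per arm (the SAP does not say). On that assumption one recording decision can move a term into or out of the table.

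If a fraction *r* of true events is recorded in every arm alike, the visible difference is *r* × (p1 − p0), where p1 and p0 are the true incidences on drug and placebo. As *r* runs from 0 to 1, the visible difference runs from none to the full difference. The ratio p1/p0 does not change while *r* is above 0. The documents give no value for *r*, p1 or p0.

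**The case against.** The strongest defence is that the sentences can be read together: report events that result from progression, but do not log progression of a known condition as an event in itself. The first sentence does speak of adverse events resulting from progression, which gives this reading some support. But the protocol does not state it. The exception also attaches to a complication, which is a consequence of the disease, so the two sentences still collide.

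A second defence is that 6.1 is the general definition and 6.3 the specific recording rule, so an exception found only in 6.3 need not be an error. That may reconcile 6.3 with 6.1. It does not reconcile 6.3 with itself, and it leaves the exception undefined.

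Third, much is captured elsewhere, and this stands. Chemistry, including eGFR and glucose, and HbA1c are collected on schedule, and SAP 7.2 gives chemistry shift and change-from-baseline summaries. Worsening pain is captured daily on the NPRS and in rescue use. A reader might infer that declining kidney function, loss of glycemic control or worse pain would go unseen; the documents do not support that.

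Fourth, sites are blinded during treatment, so differing site habits should not by themselves favour an arm, and safety is summarised without formal tests. This also stands. However, equal under-recording still shrinks a true absolute difference, and a descriptive comparison relies on complete counts.

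**Conclusion.** The contradiction is real, stands in current text and should be corrected. Protocol 6.3 gives opposite instructions on progression of a pre-existing disease and does not define the term on which they turn. One of the two also conflicts with 6.1, 6.1.2, 5.1.4 and SAP 7.1. What is affected is clinical worsening that depends on the AE form, such as new sensory loss, worsening retinopathy or a hospitalised diabetic complication, together with SAE reporting of such events. The AE part of the primary safety endpoint is weakened; its laboratory, vital sign, ECG and weight parts are not.

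Three stronger conclusions are tempting and not supported:

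- That sites cannot count these events consistently. The text shows only that two sites may both follow 6.3 and differ.
- That a particular share of events will be lost. The documents give no incidence and no rate of use of the exception, so no magnitude can be derived.
- That the exception favours the drug. Nothing in the documents shows a difference in recording between blinded arms.

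The conclusion rests on the visible text. The eCRF completion guidance is not among the documents and may already narrow the practice, but the protocol itself would still need to agree.

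**What to change.** Reconcile the sentences in Protocol 6.3 with each other and with 6.1. The simplest way is to delete the bracketed exception from the sentence on worsening or complication. Any worsening that meets the 6.1 definition is then recorded, and disease progression is weighed only at the causality step in 6.3.4.

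If the sponsor prefers to keep an exception:

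- define it narrowly, for example as NPRS diary pain scores alone;
- state that it never applies to an event that meets a seriousness criterion;
- tabulate the excluded events by arm in the SAP.

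The deletion costs one phrase in the protocol and a memo to sites. The downside is somewhat more AE records. Keeping an exception costs more, because the excluded events must still be collected so that they can be tabulated. The same 6.3 text governs Part 2, whose separate SAP is still to be written, so the change can be carried into that plan.

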#### **5.1.6.** Adverse Events

Investigators and study staff are responsible for detecting, documenting, and reporting AEs and SAEs. For each subject, reporting of AEs and SAEs begins after written informed consent/assent is provided. Throughout the study, subjects will be provided opportunities to report AEs. For more information on AEs, see Section 6.3.

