## **6.3.3.** Follow-up of Unresolved Adverse Events

All drug-related (Section 6.3.4) AEs, including CS abnormal laboratory test results reported or observed during the study, must be followed to resolution (either return to baseline or within normal limits). All other AEs or non–drug-related abnormal laboratory results will be followed through the final visit (ie, EOS or early termination). Information to be collected includes type of event, date of onset, date of resolution, Investigator-specified assessment of severity and relationship to study drug, seriousness, as well as any action taken.

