7.1. Adverse Events

All AEs will be classified using MedDRA. In this study, only treatment emergent AEs (TEAEs) i.e. those that occurred or worsened after the first randomized dose will be analyzed. Such AEs will have an onset date on or after the date of first randomized dose or will have presented prior to the first randomized dose and subsequently worsened. Therefore, whenever an analysis of summary of AEs is mentioned, it is intended that this is in reference to treatment-emergent AEs.

Whenever possible, date/time will be used to determine whether an event is treatment emergent. If an event date (start or end) is incomplete, a TEAE will be determined assuming the most conservate way as follows:

- If onset day is missing and the month and year are the same as or after the treatment start date, then that event is considered treatment emergent.
- If both onset month and day are missing and the year is the same as or after the treatment start date, then that event is considered treatment emergent.
- If both onset date and end date are completely missing, an event will be considered as a TEAE.
- If onset date is completely missing and end date is not missing which is after the first randomized dose of study drug, an event will be considered as a TEAE.

The incidence of TEAEs will be summarized by dose level (or cohort) and overall RTA 901 as follows:

- Overall summary of TEAE
- TEAEs by primary SOC and MedDRA preferred term
- TEAEs by MedDRA preferred term
- TEAEs by MedDRA preferred term with incidence of >=2%
- SAEs by primary SOC and MedDRA preferred term
- SAEs by MedDRA preferred term
- Related SAEs by primary SOC and MedDRA preferred term
- TEAEs by maximum severity, primary SOC and MedDRA preferred term
- Related TEAEs by primary SOC and MedDRA preferred term
- TEAEs that led to discontinuation of study treatment by primary SOC and MedDRA preferred term
- TEAEs that led to study drug interruption by primary SOC and MedDRA preferred term
- TEAEs that led to withdrawal from study by primary SOC and MedDRA preferred term

TEAEs that led to death by primary SOC and MedDRA preferred term

For the summary of TEAEs by severity, primary system organ class and/or preferred term, participants will be counted only once within each primary SOC/MedDRA preferred term and will only be counted under the maximum severity.

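### For an AE already ongoing at the first randomized dose, the eCRF does not show whether it worsened afterwards, so the TEAE definition cannot be applied to it from the analysis data

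*Protocol*

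**What the plan says.** **Collection.** Protocol 5.1.6 starts AE collection at consent: "reporting of AEs and SAEs begins after written informed consent/assent is provided". Events from Screening and Run-in can therefore be open when randomized treatment begins.

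**Recording.** Protocol 6.3 says that "changes in the severity (eg, worsening or improving) should be noted in the source documents", while for the database "only the total duration and greatest severity should be recorded in the eCRF". Protocol 6.3.3 describes the information collected, which "includes type of event, date of onset, date of resolution, Investigator-specified assessment of severity", together with relationship, seriousness and action taken.

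**Classification.** Protocol 6.1.2: "Adverse events that present, or worsen in intensity or frequency, following the initiation of study treatment will be categorized as TEAEs". SAP 7.1 ties the definition to the first randomized dose and includes AEs that "will have presented prior to the first randomized dose and subsequently worsened". Apart from a run-in AE table and the listings, SAP 7.1 confines AE summaries to treatment-emergent events.

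**Causality.** Protocol 6.3.4 has this category: "Not Applicable: AE occurred prior to administration of first dose of study drug".

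**The concern.** The recording rule discards what the definition needs. To decide whether an AE that began before randomized treatment worsened on it, one must know its severity at the first randomized dose, or the date on which it changed. Neither is among the listed items.

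AE frequency, intensity and relationship form the primary safety endpoint (Protocol 2.2.1.2), and SAP 7.1 reports them mainly through TEAE tables. With arms of 64, a few misclassified events can alter how an AE comparison reads.

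**Working it through.** No power, alpha or event-count figure is involved, so there is no stated result to reproduce. The question is one of identifiability: do the eCRF fields determine TEAE status for an AE that spans the first randomized dose?

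**Inputs.** Three severity grades (Protocol 6.3.5), the recording rule (Protocol 6.3), the AE items (Protocol 6.3.3) and the TEAE definition (SAP 7.1).

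**Step 1: enumerate.** Let p be the severity up to the first randomized dose, taken as constant until then, and q the worst severity afterwards. The eCRF keeps max(p, q). The event worsened in grade if q > p.

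| p | q | eCRF severity | Worsened? |
|---|---|---|---|
| mild | mild | mild | no |
| mild | moderate | moderate | yes |
| moderate | mild | moderate | no |
| moderate | moderate | moderate | no |
| mild | severe | severe | yes |
| moderate | severe | severe | yes |
| severe | mild | severe | no |
| severe | moderate | severe | no |
| severe | severe | severe | no |

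**Step 2: read off.**
- Entry mild: 1 pattern, 0 worsened. Classifiable on grade.
- Entry moderate: 3 patterns, 1 worsened and 2 not.
- Entry severe: 5 patterns, 2 worsened and 3 not.

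All 3 worsened patterns share their entry with a pattern that did not worsen, so none can be recognised. For example, onset Day -10, end Day 30, severity severe is one and the same record whether the event was severe from the start (not a TEAE) or mild until Day 10 and severe from then (a TEAE).

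**Step 3: look for a repair elsewhere in the text.**
- Protocol 6.3 does ask for a separate entry naming a worsening, but only for conditions that predate consent: "Pre-existing conditions (present before the start of the AE collection period, prior to signed consent) are considered concurrent medical conditions".
- Protocol 6.1 treats a previous condition that has become more severe or frequent since study drug as an AE. It does not tell sites to open a second record for an AE already open, and Protocol 6.3 points the other way.
- The conservative rules in SAP 7.1 apply to incomplete dates. Here the dates are complete.
- SAP 7.1 gives no derivation of worsening.

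**Step 4: size.** The documents contain no AE rates, so the number cannot be calculated. As an illustration only, suppose 10% to 20% of the 192 Part 1 subjects have an AE ongoing at Day 1 and 10% to 25% of those AEs worsen:
- low: 192 × 0.10 × 0.10 = 1.9 subjects
- high: 192 × 0.20 × 0.25 = 9.6 subjects

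Spread evenly over three arms, that is about 0.6 to 3.2 per arm. Both rates are assumptions, and these events are lost only if classification goes by onset date.

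**The case against.** The strongest reply is that the information exists and other outputs catch much of it. Source documents hold the severity changes. SAP 5.2 tabulates treatment discontinuation and study withdrawal with reasons, without a TEAE restriction, and AE is one of the reasons in Protocol 4.6.3. SAP 7.1 lists all AEs, SAEs and AEs leading to discontinuation, withdrawal or interruption. Serious events go on a separate form (Protocol 6.4). Laboratory, vital-sign and ECG summaries do not rely on AE records. Intermittent AEs have onset and duration documented, which may partly recover worsening in frequency. The eCRF completion guideline is not among the documents and could contain a new-record rule.

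Most of this stands, and it limits the point. Four stronger readings that a reader might infer are not supported:
- *Such events vanish from every by-arm table.* They do not, for the reasons just given.
- *The loss can only hide harm from the drug.* That would require classification by onset date, which no text prescribes. A programmer could equally count every spanning AE and over-count. The recording rule also applies to placebo.
- *The run-in table would show them at a severity reached only later.* That table is by system organ class and preferred term, with no severity, and a Screening-onset AE need not be in it.
- *All pre-dose AEs carry a causality of not applicable.* Protocol 7.1 counts placebo as study drug and Protocol 7.5 starts study drug at Run-in, so this reaches Screening-onset AEs only.

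What the reply does not remove is the conflict itself. Source is not the data set that the SAP analyses, and a guideline with a new-record rule would contradict Protocol 6.3 and need reconciling with it.

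**Conclusion.** The point holds in a limited form. For AEs with onset after consent, ongoing at the first randomized dose and with greatest severity moderate or severe, treatment-emergent status by worsening cannot be determined from the eCRF as the protocol describes it. AEs resolved before that dose, AEs never above mild (on grade) and worsening of conditions that predate consent are not affected.

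If these events are classified by onset date, worsening on treatment is left out of the TEAE, related-TEAE, maximum-severity and AE-discontinuation tables. For Screening-onset AEs there is the further problem that no second record exists to carry a later causality assessment.

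The identifiability result needs no assumed rate. It does rest on reading Protocol 6.3 as one record per AE, which is an inference from its wording. The number of subjects affected is not known from the documents.

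**What to change.** **Recording from now on, including Part 2.** Amend Protocol 6.3 and align the eCRF completion guideline. When an AE ongoing at the first randomized dose worsens on or after that dose, close its record at the pre-dose severity and open a new one, worded as a worsening, with its own onset date, severity and causality. Protocol 6.3 already uses such an entry for conditions that predate consent. The single-record rule can stay for AEs that start after the first randomized dose. Cost: guideline wording, a site memo and a few more eCRF records.

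**Part 1.** SAP 6.1 already reports how many randomized patients took duloxetine, so Part 1 randomization was at least well advanced and a protocol change alone will not repair records already entered. State in SAP 7.1 how worsening is derived, by one of two routes:
- Count every AE that spans the first randomized dose with greatest severity above mild as treatment-emergent, with a sensitivity table that excludes them. Cost: a sentence, one table and possible slight over-counting, because AEs that were already moderate or severe before the dose are included.
- Obtain severity at the first randomized dose from source, for those spanning AEs only. This is more exact but needs queries to the sites concerned, out of approximately 75 planned.

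The choice should be made and documented before unblinding.
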